### **5.7.2. Serious Adverse Event**

The Investigator is responsible for ensuring that all serious adverse events observed by the clinical staff or reported by the subject that occur after signing of the informed consent through 30 days after the last day of the application of the investigational product or the end of study (whichever is later) are recorded in the subject's medical record and are submitted per SAE reporting requirements.

All SAEs will be reported to the Sponsor (or delegate) within 24 hours of becoming aware of the event, whether or not the serious events are deemed IP related. All serious event reporting will adhere to ICH E6: Guideline for Good Clinical Practice and ICH E2A: Clinical Safety Data Management: Definitions and Standards for Expedited Reporting.: The ERB/IRB will be notified of the Alert Reports as per HC, FDA, ICH and the IRB/ERB's policies and procedures. Refer to the Safety Reporting Instructions for SAE reporting.

An SAE is any AE that in the view of either the PI or Sponsor, results in any of the following outcomes: Death, a life threatening AE, inpatient hospitalization or prolongation of existing hospitalization, a persistent or significant incapacity or substantial disruption of the ability to conduct normal life functions, or a congenital anomaly/birth defect. Important medical events that may not result in death, be life threatening, or require hospitalization may be considered serious when, based upon appropriate medical judgment, they may jeopardize the subject and may require medical or surgical intervention to prevent one of the outcomes listed in the above definition. Examples of such medical events include allergic bronchospasm requiring intensive

treatment in an emergency room or at home, blood dyscrasias or convulsions that do not result in inpatient hospitalization, or the development of drug dependency or drug abuse.

Life threatening is defined as an AE that in the view of the PI or Sponsor, places the subject at immediate risk of death. It does not include an AE that, had it occurred in a more severe form, might have caused death.

Hospitalization does not include the following:

- Rehabilitation facilities, hospice facilities or respite care (e.g., caregiver relief)
- Nursing homes or skilled nursing facilities
- Emergency room visits
- Same day surgeries (as outpatient/same day/ambulatory procedures)
- <24 hour admissions for observation or evaluation

Hospitalization or prolongation of hospitalization in the absence of a precipitating, clinical AE is not in itself an SAE. Examples include:

- Admission for treatment of a preexisting condition that did not worsen
- Hospitalizations for cosmetic elective surgery, social, and/or convenience admissions
- Pre-planned treatments or surgical procedures should be noted in the history documentation for the individual subject
- Diagnostic and therapeutic procedures, such as surgery, should not be reported as AEs; however, the medical condition for which the procedure was performed should be reported if it occurs during the reporting period and meets the definition of an AE. For example, an acute appendicitis that begins during the AE reporting period should be reported as an AE, and the resulting appendectomy should be recorded as treatment of the AE.

Unexpected is defined as an AE that is not listed in the IB or is not listed at the specificity or severity that has been observed; or is not consistent with the risk information described in the general investigational plan or elsewhere in the current study documentation.

If an SAE occurs to a subject on this study, contact the Medical Monitor within one business day of knowledge of event.

The definitions and reporting requirements of Health Canada/the Food and Drug Administration (FDA)/ICH Guidelines for Clinical Safety Data Management, Definitions and Standards for Expedited Reporting, Topic E2A will be adhered to. If any AEs are serious, as defined by ICH Guidelines for Clinical Safety, required procedures will be followed.

### **5.7.3. Suspected Unexpected Serious Adverse Reaction (SUSAR)**

This is defined as a serious adverse reaction, the nature or severity of which is not consistent with the known study treatment information. A serious event or reaction is not defined as a SUSAR when: 'it is serious but expected' or it does not fit the definition of an SAE, whether expected or not.

### **5.7.4. Safety Review with Subject**

At each follow-up visit, subjects will be queried with an open-ended question such as: 'How have you been feeling since your last visit?' Additionally, the study staff will review subject diaries and, if it appears that a potential AE was recorded, study staff will query the subject and determine if an AE occurred.

Where appropriate, medical test(s) and/or examination(s) will be performed to document resolution and/or outcome of event(s).

### **5.7.5. Adverse Event Reporting**

The Investigator is responsible for ensuring that all adverse events observed by the clinical staff or reported by the subject that occur after baseline the first application of investigational product through the end of the study are recorded in the subject's medical record and the eCRF.

AEs (whether serious or non-serious) and clinically significant abnormal laboratory test value(s) will be evaluated by the PI and treated and/or followed up for up to 30 days after end of treatment or until the symptoms or value(s) return to normal, or acceptable levels, as judged by the PI.

The Investigator will review each event and assess its relationship to investigational product treatment (unrelated, unlikely, possibly, probably, likely) or phototherapy treatment (unrelated, likely). Each sign or symptom reported will be graded on the NIH NCI CTCAE (Version 5.0) toxicity grading scale 5-point severity scale (Grade 1, 2, 3, 4 and 5). The date and time of onset, time relationship to drug dosing and/or phototherapy treatment, duration, and outcome of each event will be noted.

The relationship of each AE to the **investigational product** will be assessed using the following definitions:

Unrelated	
The AE must clearly be caused by the subject's clinical state, or the study procedure/conditions.
 
Definitely not related to drug.
 
Temporal sequence of AE onset relative to administration of drug not reasonable.
 
Another obvious cause of an AE.

Unlikely	
Time sequence is unreasonable.
 
There is another more likely cause for an AE.

Possibly	
Corresponds to what is known about the drug.
 
Time sequence is reasonable.
 
Could have been due to another equally, likely cause.

Probably	Is a known effect of the drug. Time sequence from taking drug is reasonable. Ceases on stopping the drug. Cannot be reasonably explained by the known characteristics of the subject's clinical state.
Likely	Is a known effect of the drug (e.g., listed in Physicians' Desk Reference, Compendium of Pharmaceuticals and Specialties, IB). Time sequence from taking drug is reasonable. Event stops upon stopping drug, event returns upon restarting drug.

The relationship of each AE to the **phototherapy treatment** will be assessed using the following definitions:

Unrelated	The AE must clearly be caused by the subject's clinical state, or the study procedure/conditions. Definitely not related to phototherapy treatment. Temporal sequence of AE onset relative to phototherapy treatment not reasonable. Another obvious cause of an AE.
Likely	Is a known effect of the phototherapy treatment (e.g., listed in Fitzpatrick's Dermatology, 9 th Edition). ( Kang 2019 ) Time sequence from the phototherapy treatment is reasonable. Event stops upon cessation of phototherapy treatment, event returns upon restarting phototherapy treatment.

The following CTCAE toxicity grading scale 5-point severity scale definitions for rating maximum severity will be used:

Grade 1	Mild; asymptomatic or mild symptoms; clinical or diagnostic observations only; intervention not indicated.
Grade 2	Moderate; minimal, local or noninvasive intervention indicated; limiting age-appropriate instrumental activities of daily living.*
Grade 3	Severe or medically significant but not immediately life-threatening; Hospitalization or prolongation of hospitalization indicated; disabling; limiting self-care activities of daily living.** Note: An experience may be severe but may not be serious, e.g., severe headache).
Grade 4	Life-threatening consequences; urgent intervention indicated.
Grade 5	Death related to AE.

Note: A semi-colon indicates 'or' within the description of the grade.

\* Instrumental activities of daily living refer to preparing meals, shopping for groceries or clothes, using the telephone, managing money, etc.

\*\* Self-care activities of daily living refer to bathing, dressing and undressing, feeding self, using the toilet, taking medications, and not bedridden.

The Investigator is responsible for the assessment of all adverse events to determine if the event is related to the Investigational Product, Phototherapy Treatment, or both. AEs will be coded using the most current MedDRA® version available at the start of the study (e.g., 21.0 or higher).

## **5.8. Reporting Pregnancy**

During the study, all subjects should be instructed to contact the Investigator immediately if they suspect they might be pregnant (e.g., missed or late menstrual period). If pregnancy is confirmed, Investigational Product must be discontinued immediately, the subject should be referred to an obstetrician experienced in reproductive toxicity for evaluation and counseling, and the subject should be followed until conclusion of the pregnancy. Subject may be required to sign a separate informed consent form to obtain pregnancy follow-up information, per local requirements.

The Investigator is responsible for reporting all available pregnancy information on the pregnancy report and submitting to the Medical Monitor within 24 hours of becoming aware of the event, although pregnancy itself is not considered an AE. Follow-up information detailing the outcome of the pregnancy and the health of the newborn should be reported as it becomes available. Any pregnancy resulting in a congenital abnormality or birth defect of the newborn, or neonatal death occurring within 30 days of the birth must be reported as a SAE, regardless of causality. Any infant death that occurs after the 30-day reporting period that the Investigator suspects is related to Investigational Product must also be reported as an SAE.

Partner pregnancies of a male subject will be reported.

## **5.9. Treatment Stopping Rules**

If a subject has non-cutaneous adverse events of concern, clinically significant laboratory values or any condition that the Investigator determines could possibly be related to the investigational product, the Investigator should immediately contact the Medical Monitor to discuss if the subject should be discontinued from treatment with investigational product.

Treatment for any individual subject should be interrupted if the Investigator observes the following:

- If a subject develops an application site reaction with the clinical appearance of an ‘irritation reaction’, and with a severity of a Dermal Response Score of 5 (erythema, edema, and papules) on Local Tolerability Assessment ([Section 5.1.8](#)), treatment should be interrupted for up to one week and may then be resumed if the reaction has, in the opinion of the Investigator, adequately resolved.

For application site reactions treatment should be discontinued:

- If the application site reaction reoccurs, treatment should be discontinued permanently, and the subject followed until the reaction resolves.

Treatment for any individual subject will be discontinued if the subject experiences:

- A serious adverse event (SAE) or a clinically significant non-serious AE which in the opinion of the Principal Investigator or Medical Monitor warrants discontinuation from the study for that subject's well-being.
- A treatment-emergent severe (Grade 3) laboratory abnormality (confirmed by repeat sample) which in the opinion of the Principal Investigator or Medical Monitor warrants discontinuation from the study for that subject's well-being.
- A severe infection (Grade 3 or higher)
- An ischemic or thromboembolic cardiovascular event (regardless of Grade)
- A severe adverse event within the system-organ class of Cardiac Disorders (Grade 3 or higher)

As noted above, study treatment must be discontinued immediately in the event of a female subject's pregnancy.

In the event of a medical emergency where unblinding is required to provide medical care to the subject, refer to the most current IRT plan and Breaking Treatment Codes ([Section 4.4.1](#)). Contact the Medical Monitor and the Sponsor promptly.

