### **5.1.8. Local Tolerability Assessment**

The Investigator Local Tolerability Assessments will be performed according to the Schedule of Visits and Assessments ([Section 1.3](#)). Application site reactions are graded using the scale detailed in the following section ([Berger 1982](#)).

The Investigator Local Tolerability Assessment will be conducted by the Investigator **prior to investigational product application** in the clinic.

**Investigators will specify if any application site reaction is due, in whole or in part, to the effects of phototherapy treatment.**

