#### Dermal Response

0. no evidence of irritation
1. minimal erythema, barely perceptible
2. definite erythema, readily visible; minimal edema or minimal papular response
3. erythema and papules
4. definite edema
5. erythema, edema, and papules
6. vesicular eruption
7. strong reaction spreading beyond application site

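### The only visible score-based interruption rule for application site reactions names Dermal Response Score 5 without 'or higher', so scores 6 and 7 are left to judgement

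*Protocol*

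**What the plan says.** Protocol Section 5.9 gives one interruption rule tied to a dermal score. It applies when a reaction looks like irritation and occurs "with a severity of a Dermal Response Score of 5 (erythema, edema, and papules) on Local Tolerability Assessment". Treatment should then be paused for up to one week and may restart once the Investigator considers the reaction adequately resolved. A second rule makes discontinuation permanent if the reaction comes back.

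The score comes from Section 5.1.8, which states: "Application site reactions are graded using the scale detailed in the following section". The Dermal Response scale runs from 0 to 7. Score 5 is the level named in the rule. Score 6 is "vesicular eruption" and score 7 is "strong reaction spreading beyond application site".

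Section 5.9 also has general provisions. For non-cutaneous events of concern, significant laboratory values, or any condition judged possibly related to the product, "the Investigator should immediately contact the Medical Monitor to discuss if the subject should be discontinued from treatment with investigational product". Treatment is also to be discontinued for an SAE or clinically significant AE that the Principal Investigator or Medical Monitor believes warrants it. Section 4.6 separately lists reasons for which a subject may stop the product.

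**The concern.** A severity threshold normally acts at the named level and at everything worse. This one is written as a single value, and its parenthetical repeats the description of score 5 alone. The descriptions of 6 and 7 name different signs, so a vesicular or spreading reaction is not literally a score-5 reaction. Followed to the letter, the rule prescribes a pause for the milder reaction and nothing for a first reaction at the two worse levels.

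What is at stake is consistency of subject protection. The summary of changes records that Amendment 1 brought in a stopping rule based on the Investigator's dermal rating. Adding a score-based rule to opinion-based handling gives sites a common action, and at scores 6 and 7 the text does not supply one. With approximately 50 sites planned (Section 4.3), a safety rule should not depend on each site inferring the missing words.

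**Working it through.** There is no figure in the plan to reproduce. The check maps each score in Section 5.1.8 to the action in Section 5.9 for a first reaction, then looks for any other visible text that fills a gap.

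**Score-to-action map, read literally**

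| Dermal Response score | Score-based action, current text | With '5 or higher' |
|---|---|---|
| 0 to 4 | none | none |
| 5 | interrupt, up to one week | interrupt |
| 6 | none | interrupt |
| 7 | none | interrupt |

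The scale has 8 levels. Levels at or above the trigger: 5, 6 and 7, so 3. Covered by the rule: 1. Not covered: 3 − 1 = 2.

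**Does other visible text cover a first reaction at 6 or 7?**

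- *Recurrence rule, Section 5.9.* It needs an earlier reaction, so it cannot govern a first one.
- *Medical Monitor contact, Section 5.9.* The sentence begins with non-cutaneous events. A skin reaction enters only as a condition possibly related to the investigational product. The duty is to discuss discontinuation; no pause is prescribed. Section 5.1.8 has Investigators say whether a reaction is due to phototherapy, and one attributed wholly to phototherapy could miss this route.
- *SAE or clinically significant AE bullet, Section 5.9.* It acts only when someone judges that discontinuation is warranted, a higher bar than a pause. Section 5.7.1 helps bring irradiated site reactions into the AE route.
- *Section 4.6.* Its wording is permissive. Its AE item points back to Section 5.9, but a separate item covers medical conditions that, in the Investigator's opinion, prevent adherence. A serious skin reaction could qualify.
- *SAP Section 9.2.* It summarises the scores and sets no action.

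So three provisions can reach scores 6 and 7, and all three depend on opinion. None is score-based.

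**How does Section 5.9 write its other thresholds?** Four bullets refer to a grade:

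| Bullet | Upward reach stated? |
|---|---|
| Infection: "A severe infection (Grade 3 or higher") | yes |
| Cardiac: "A severe adverse event within the system-organ class of Cardiac Disorders (Grade 3 or higher") | yes |
| Cardiovascular: "An ischemic or thromboembolic cardiovascular event (regardless of Grade") | yes |
| Laboratory abnormality, Grade 3 | no |

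Three of four state their reach. The laboratory bullet does not, although the CTCAE scale in Section 5.7.5 runs to Grade 5. The drafting is uneven, which points to an oversight more than to a deliberate cap at 5.

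**When can the rule act?** Section 1.3 schedules tolerability assessment on Days 1, 29, 57, 85, 113, 141 and 169, which is 7 visits. Six follow the first treatment. Treatment is still to continue at 5 of them (Weeks 4 to 20; product is last dispensed at Week 20). Five is the number of scheduled occasions, not a ceiling: Section 5.9 speaks of what the Investigator observes, Section 5.1 allows extra safety assessments at the Investigator's discretion, and Section 5.6 allows unscheduled visits for AE follow-up.

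The documents give no expected rate of scores 6 or 7, so the number of subjects who might have been affected cannot be estimated.

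**The case against.** The strongest reply is that nobody would apply the rule literally. An Investigator who pauses treatment for erythema, edema and papules will not continue through blistering because two words are missing, and the bare Grade 3 in the laboratory bullet shows that Section 5.9 can state a minimum without saying so. This largely stands. It lowers the practical risk and weakens any argument from the contrast with the other bullets. It does not put the missing rule into the text, and it supports making the wording match the evident intent.

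A reader might infer that a subject with a score of 6 or 7 had no safeguard, or was expected to continue treatment. The documents do not support that. The judgement-based provisions reach those scores, and the AE bullet leads to discontinuation, a stronger action than a pause. Nor is the score-5 rule itself strictly mandatory: it says treatment should be interrupted, it depends on the reaction looking like irritation, and restart rests on the Investigator's opinion. The contrast is between a score-based rule and none.

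A reader might also infer that 6 and 7 were left out on purpose, because restart after a week suits them less well. That is possible, but no visible text says so. It is a sound reason not to carry the score-5 restart terms up the scale without thought.

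Finally, Appendix 1, the NB-UVB treatment protocol, is redacted. It may contain holds for phototherapy reactions, so no absence can be claimed beyond the visible text.

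**Conclusion.** The point holds as a minor safety-wording correction. In the visible text, the one score-based interruption rule covers score 5 and omits the two worse scores. A first reaction at 6 or 7 is left to Medical Monitor contact, the clinically significant AE bullet and the Section 4.6 criteria.

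This rests on a literal reading of Section 5.9 and on the unredacted text only. The practical effect is probably small, since most investigators would read 5 as a minimum.

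It would be wrong to infer any effect on the trial's results or on subjects now in the study. The SAP plans descriptive summaries with no formal testing (Sections 4.1 and 6), and it records that the study was terminated and enrolled subjects were early terminated (Sections 3 and 10). The correction matters for the written rule and for any later protocol that reuses it.

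**What to change.** In protocol Section 5.9, change the trigger to 'a Dermal Response Score of 5 or higher', with interruption as the minimum action.

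Two matters are for the clinical team to decide and state:

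- whether a reaction at 6 or 7 needs Medical Monitor agreement before restart, or permanent discontinuation, instead of the current restart terms for score 5;
- whether the irritation qualifier applies at 6 and 7, since a vesicular or spreading reaction judged not to be irritation would otherwise still fall outside the rule.

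The cost is one or two sentences in Section 5.9. Data collection, visits, sample size and analysis are unchanged.

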## **6. STATISTICAL METHODS**

Data will be handled and processed according to the Contract Research Organization's Standard Operating Procedures, which are written based on the principles of GCP.

### **6.1. Statistical Methods**

The methodology presented below is a summary of the more detailed analysis plan that will be presented in the Statistical Analysis Plan (SAP). The SAP will be finalized before the database is locked and unblinded. Any changes to the methods described in the final SAP will be described and justified in the clinical study report.

All statistical processing will be performed using SAS® (Version 9.4) unless otherwise stated.

Descriptive statistics will be used to provide an overview of the safety, efficacy, and pharmacokinetic results. For categorical parameters, the number and percentage of subjects in each category will be presented. The denominator for percentage will be based on the number of subjects appropriate for the purpose of analysis. For continuous parameters, descriptive statistics will include n (number of subjects), mean, standard deviation (SD), median, minimum, and maximum.

Missing efficacy data for F-VASI will be imputed using multiple imputation.

For statistical comparisons other than those for the primary and hierarchical secondary endpoints, the overall 0.05 significance level will be used and no adjustments will be made for multiple comparisons.

### **6.1.1. Pharmacokinetics Assessment**

Plasma pre-dose concentrations will be compared between treatment groups to evaluate potential differences.

### **6.1.2. Determination of Sample Size**

The primary statistical comparison will be to compare

- ARQ-252 cream 0.3% in combination with phototherapy vs. vehicle cream in combination with NB-UVB
- ARQ-252 cream 0.3% in combination with phototherapy vs. ARQ-252 cream 0.3% in combination with sham phototherapy at the 5% significance level.

A sample size of 500 subjects will provide approximately 84% power to detect an ARQ-252 cream 0.3% in combination with phototherapy response rate of at least 50% vs. a vehicle cream in combination with phototherapy response rate of 30% and approximately 84% power to detect an ARQ-252 cream 0.3% in combination with phototherapy rate of at least 50% vs. an ARQ-252 cream 0.3% in combination with sham phototherapy rate of 30% using a stratified Cochran-Mantel-Haenszel test conducted at the 0.025 alpha level for each comparison. A drop out rate of 15% at 24 weeks is assumed.

Upon successful testing for the comparisons above, a hierarchical testing scheme will be used to test the following secondary comparisons:

- ARQ-252 cream 0.3% in combination with phototherapy vs. vehicle cream BID in combination with the sham phototherapy
- ARQ-252 cream 0.3% in combination with sham phototherapy vs. vehicle cream BID in combination with the sham phototherapy
- Vehicle cream BID in combination with phototherapy vs. vehicle cream BID in combination with the sham phototherapy

Assuming a Vehicle cream BID in combination with the sham phototherapy rate of no more than 5%, these comparisons are expected to have at least 74% power. These comparisons will be made at either the 0.025 or 0.05 level, depending on the outcome of the primary statistical comparisons.

